5.7 Duration of follow-up

All patients, including those who discontinue protocol therapy early, will be followed for response until progression or one year from registration, whichever occurs first. Patients will then be followed for survival for five years from the date of registration. All patients must also be followed through completion of all protocol therapy.

Safety and Immunologic Activity of Multiple Infusions of APN401
Wake Forest Baptist Comprehensive Cancer Center
CCWFU 03716

6.0

Study Calendar

Baseline evaluations, including imaging, are to be conducted within 4 weeks prior to initiation of treatment (Day 0). In the event that the patient's condition is deteriorating, laboratory evaluations should be repeated within 48 hours prior to initiation of the next cycle of therapy.

		Treatment Phase							Follow-Up Phase		Early Termination
	Pre-Study ^J	Day 0 Week 1	Day 1 Week 1	Day 15 Week 3 (± 1 day)	Day 28 Week 5 (± 3 days)	Day 29 ^N Week 5	Day 56 Week 9 (± 3 days)	Day 57 ^N Week 9	Day 71 Week 10 (± 3 days)	Week 18 and every 8 weeks (± 1 week) ^L	Off Study Visit/Early Termination Visit ^{L,M}
Leukapheresis ^A		X			X		X				
APN401 ^B			X			X		X			
Informed consent	X										
Demographics	X										
Medical history	X										
Concurrent meds		X			X		X		X	X ^O	X
Vital signs ^C	X	X	X	X	X	X	X	X	X	X	X
Physical exam ^Q	X	X		X	X		X		X	X	X
Performance status	X	X		X	X		X		X	X	X
CBC w/diff ^D	X	X		X	X		X		X	X	X
Chemistries ^E	X	X		X	X		X		X	X	X
PT, PTT	X										
HIV, HBV, HCV	X										
βhCG ^F	X										
Adverse events		X	X	X	X	X	X	X			X
Imaging ^G	X								X ^L	X ^K	X ^L
Tumor marker ^H	X								X	X	X
Immune response ^I		X		X	X		X			X	X

A. PBMC will be harvested from the peripheral blood by a standard 1.5 to 2.0 blood volume mononuclear cell leukapheresis.

B. APN401 is infused 50 x10⁵/kg IV over 30 minutes

C. Vitals signs should include blood pressure, heart rate, temperature, and respiratory rate. At the administration visits, vital signs should also be performed before infusion and 30 and 60 minutes after the end of the infusion.

D. Hemoglobin, hematocrit, white blood cell count, and platelets. The CBC differential includes enumeration of neutrophils, lymphocytes, eosinophils, monocytes, basophils and any abnormal blood cells.

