9.3.2 Evaluation of non-target lesions

- Complete Response (CR): Disappearance of all non-target lesions and normalization of tumor marker level
- Incomplete Response/Stable Disease (SD): Persistence of one or more non-target lesion(s) or/and maintenance of tumor marker level above the normal limits
- Progressive Disease (PD): Appearance of one or more new lesions and/or unequivocal progression of existing non-target lesions
- Although a clear progression of “non-target” lesions only is exceptional, in such circumstances, the opinion of the treating physician should prevail, and the progression status should be confirmed at a later time by the review panel (or study chair).

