9.4 Confirmatory measurement/duration of response

- 9.4.1 Confirmation: To be assigned a status of PR or CR, changes in tumor measurements must be confirmed by repeat assessments that should be performed four weeks after the criteria for response are first met. In the case of SD, follow-up measurements must have met the SD criteria at least once after study entry at a minimum interval of eight weeks.
- 9.4.2 Duration of overall response: The duration of overall response is measured from the time measurement criteria are met for CR or PR (whichever is first recorded) until the first date that recurrent or progressive disease is objectively documented (taking as reference for progressive disease the smallest measurements recorded since the treatment started). The duration of overall CR is measured from the time measurement criteria are first met for CR until the first date that recurrent disease is objectively documented.
- 9.4.3 Duration of stable disease: Stable disease is measured from the start of the treatment until the criteria for progression are met, taking as reference the smallest measurements recorded since the treatment started.

Safety and Immunologic Activity of Multiple Infusions of APN401
Wake Forest Baptist Comprehensive Cancer Center
CCCWU 03716

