11.1.2 Secondary Outcome

- To determine the immunologic effects of multiple infusions of APN401 through monitoring immune response in vitro by measuring IFN production, frequency of immune cells, and neutrophil to lymphocyte ratio for one year.
- To document clinical response and survival using from RECIST criteria and progression free survival and overall survival for five years, respectively.

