11.4 Analyses

Adverse events will be categorized by organ system and severity and summarized as frequency counts and percentages. Other categorical data, such as clinical response, will be summarized similarly. Measured data, such as immune response, will be summarized as medians and ranges. All tests of statistical significance will be 2-sided and p-values will generally not be adjusted for multiple comparisons.

11.4.1 **Toxicity:** APN401 will be considered tolerable if $\leq 1/6$ or if overall $\leq 3/12$ patients (i.e. an observed toxicity rate of at most 30%) experience grade 3-4 toxicity. With this design the likelihood of stopping early and rejecting the therapy as too toxic is $\leq 11.4\%$ if the true grade 3-4 toxicity rate is $\leq 10\%$ and $> 76.7\%$ if it is $> 40\%$. The overall likelihood of declaring APN401 too toxic is $\leq 1.2\%$ and $> 62\%$, respectively in these scenarios.

11.4.2 **Immune response:** APN401 will be considered immunologically active if PBMC IFN- γ production in response to anti-CD3/28 stimulation or to one or more tumor antigens is significantly increased or if neutrophil to lymphocyte ratio is significantly decreased post-therapy (week 9) compared to pre therapy. Immune responses will be summarized as medians and ranges. The effects of treatment on these markers individually will be analyzed using paired t-tests or the non-parametric counterpart. With 12 patients there will be statistical power equal to 80% to detect 1 standard deviation change in these markers following treatment. All tests will be 2-sided and $P < 0.05$ will be considered significant.

Safety and Immunologic Activity of Multiple Infusions of APN401
Wake Forest Baptist Comprehensive Cancer Center
CCCWU 03716

11.4.3 Clinical response and survival: Clinical response will be assessed by RECIST and summarized as frequency counts and percentages. Progression-free survival and overall survival are calculated from the initial infusion to confirmation of progression or death. Exploratory survival plots will be estimated using the Kaplan Meier approach and median PFS and OS will be estimated if enough events occur.

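### Section 11.4.3 gives PFS and OS one shared end clause, so one of the two is misdefined on either reading, and it leaves confirmation of progression undefined

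*Combined protocol and SAP*

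**What the plan says.** The only definition of either endpoint is in Section 11.4.3: "Progression-free survival and overall survival are calculated from the initial infusion to confirmation of progression or death". The same section plans Kaplan-Meier plots, described as exploratory, and adds that "median PFS and OS will be estimated if enough events occur".

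Other sections name the endpoints or set follow-up without defining an event:

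- Section 11.1.2 lists the outcome: "To document clinical response and survival using from RECIST criteria and progression free survival and overall survival for five years, respectively".
- Section 5.7 ends response follow-up at progression or one year, then states: "Patients will then be followed for survival for five years from the date of registration".

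Dates of progression appear only in the response section:

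- Section 9.4.2 runs duration of response "until the first date that recurrent or progressive disease is objectively documented".
- Section 9.4.3 says: "Stable disease is measured from the start of the treatment until the criteria for progression are met".
- Section 9.4.1 sets a repeat-assessment requirement for response: "To be assigned a status of PR or CR, changes in tumor measurements must be confirmed by repeat assessments". It sets none for progressive disease.
- Section 9.3.2 covers the exceptional case of progression in non-target lesions only. The treating physician's opinion prevails, and a review panel or the study chair confirms it later.

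**The concern.** PFS and OS normally differ in their events: progression or death for PFS, death alone for OS. Here one origin and one end clause serve both, and an analyst has no other text to work from. Two analysts could follow the sentence faithfully and produce different data sets.

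The clause also ties the progression event to its confirmation, whereas the response section dates progression when it is first documented or when the criteria are met. One patient's progression could then carry one date for duration of response or stable disease and a later one for PFS. With at most 12 patients, re-dating one or two of them can move a Kaplan-Meier median.

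**Working it through.** The plan states no event count, power or expected median for PFS or OS, so there is no figure to reproduce. The check is a comparison of texts, followed by the size of the possible date shift.

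**1. The ways to read the sentence in 11.4.3**

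| Reading | PFS event | OS event | Result |
|---|---|---|---|
| Clause applies to each endpoint | progression or death | progression or death | OS is the same variable as PFS |
| Clause is split in order | progression | death | OS is right; PFS omits death |

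The usual pair (PFS to progression or death, OS to death) needs death to serve both endpoints and progression only one. The sentence yields that under neither reading.

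**2. Comparison with the rest of the plan**

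Under the first reading the two planned medians would be identical, and the five-year survival follow-up would add nothing for a patient who had already progressed. Both features point to OS ending at death. They show the intent for OS but do not repair PFS under the second reading.

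**3. What confirmation could mean**

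- Target-lesion or new-lesion progression (9.3.1): no repeat assessment is required.
- PR or CR (9.4.1 and Study Calendar note G): a repeat at four weeks is required.
- Non-target-only progression (9.3.2): later confirmation is required, with no interval and no rule on which date counts.
- Study Calendar note L: observation ends at objective progression, so no confirming scan is scheduled after it.

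**4. Size of the possible shift in the PFS date**

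Shift = date of confirmation minus date first documented. Relative shift = shift divided by time from first infusion to first documentation.

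Inputs: the first infusion is on Day 1 and the first on-study scan on Day 71, so (71 − 1)/7 = 10 weeks. The next scan is at week 18, about 8 weeks later, and scans then follow every 8 weeks. The meaning of confirmation is assumed in each row.

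| Assumed meaning | Shift | Progression at 10 weeks | Progression at 18 weeks |
|---|---|---|---|
| Objective documentation | 0 | 0% | 0% |
| Repeat at the response interval | 4 weeks | 4/10 = 40% | 4/18 = 22% |
| Next scheduled scan | about 8 weeks | 8/10 = 80% | 8/18 = 44% |

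**5. Illustration on assumed medians**

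Progression and death times were simulated as independent exponentials (400,000 draws) on the scan schedule of about week 10, week 18, then every 8 weeks. The medians in the first column are assumptions. All times are in weeks.

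| Assumed median progression / death | PFS, first documented | PFS, 4 weeks later | PFS, next scan | OS, death only | Share of OS events that are progression under the shared clause |
|---|---|---|---|---|---|
| 8 / 26 | 10.1 | 14.1 | 18.0 | 26.0 | 66% |
| 13 / 26 | 10.1 | 14.1 | 18.0 | 25.9 | 58% |
| 13 / 52 | 11.3 | 14.1 | 18.0 | 51.8 | 73% |
| 26 / 52 | 18.0 | 22.0 | 26.0 | 52.0 | 57% |

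The last column dates progression at first documentation. Under the shared clause the reported OS median would equal the PFS median: about 10 to 18 weeks, against 26 to 52 weeks for death alone.

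**The case against.** The strongest reply is that this is loose drafting with a clear intent. The plan lists PFS and OS as separate outcomes, plans a median for each, and follows patients for survival long after progression follow-up ends. A competent analyst would run OS to death. That stands. A reader might infer that the plan has decided to count progression as an OS event, which would make OS uninterpretable. The documents do not support that. They support an ambiguous sentence, and the surrounding text points away from such a decision.

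A second reply concerns dating. A reader might infer that PFS is dated late, by 40% to 80%, or that a patient whose progression is never confirmed would be carried to the date of death. Neither is established. Since no repeat scan is scheduled after progression, confirmation may simply mean objective documentation, in which case the shift is zero. Section 9.4.2 governs duration of response, not PFS, so it is not a PFS rule that 11.4.3 breaks. Section 9.3.2 also gives the word some basis for non-target-only progression. The 40% and 80% figures apply only to progression at the first scan, under assumed meanings of confirmation.

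A third reply is that little depends on these endpoints. No test, threshold or stopping rule uses them: 11.4.1 concerns toxicity and 11.4.2 immune response. That stands and limits the weight of the point.

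None of this supplies a reading under which both endpoints are correctly defined.

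**Conclusion.** The sentence in 11.4.3 is wrong as written, because one endpoint is misdefined on either reading and no other section corrects it. The intent for OS is recoverable from context. The intended handling of death in PFS, and the date assigned to progression, are not stated.

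The effect of the undefined confirmation on PFS runs from 0 to about 8 weeks. That range rests on assumed meanings and on the main scan calendar; the plan does not say which meaning applies. The simulated medians also rest on assumed event rates and show direction and scale only.

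The impact is modest, because PFS and OS are secondary, descriptive and untested, with at most 12 patients. The correction is still worth making, ideally before event dates are derived.

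**What to change.** Replace the sentence in 11.4.3 with separate definitions:

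- OS runs from the initial infusion to death from any cause, otherwise censored at the date last known alive.
- PFS runs from the initial infusion to the first objectively documented progression under Section 9.3 or death from any cause, whichever comes first, otherwise censored at the last tumour assessment.
- Progression in non-target lesions alone, once confirmed under 9.3.2, is dated to when it was first documented.

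This aligns PFS dates with the dating already used in 9.4.2 and 9.4.3. The cost is two rewritten sentences and one added rule, with no new visits, scans or patients. The downside is that reported PFS may be shorter than under a later confirmation date, or than under a definition that leaves out death.

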11.5 Interim Analysis

As described above an interim analysis will occur after 6 patients are enrolled

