5.0 Treatment Plan

5.1 Dosing

- 5.1.1 Leukapheresis to collect PBMC for infusion will be performed the day prior to infusion. Patients will be administered three infusions of APN401 at 50×10^6 cells/kg IV, separated by 4 weeks (reference Appendix I). Leukapheresis and administration of APN401 can be delayed up to 3 weeks at the physician's discretion. Subsequent treatment must occur 28 days after prior treatment.
- 5.1.2 Six patients will be treated initially. Should >1/6 subjects experience greater than grade 3 or 4 toxicity, further enrollment of study subjects and further administration of the study agent will stop pending assessment of the risk.
- 5.1.3 If DLT is observed in $\leq 1/6$, than an additional four patients (a total of 12) will be enrolled to allow evaluation of laboratory correlates. Enrollment will be suspended if >1/6 or >3/12 patients manifest DLT

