11.3.2 Sample size

A total of up to 12 patients will be treated to allow evaluation of laboratory correlates. The design allows for an interim analysis to occur after the first 6 patients are enrolled. If 1 or less experience a grade 3-4 toxicity then 4 more will be enrolled, if 3 or less experience a grade 3-4 toxicity the agent will not be considered too toxic. With this sample size, during the first stage of the trial, if the true toxicity rate is 10% (or less) the trial will stop with 11% probability, whereas if the true toxicity rate is 40% (or higher) then the trial will stop with 76.7% probability. Likewise, if the trial continues to 12 patients, if the true toxicity rate is 10% or less the probability of observing more than 3 toxicities is 1.2% and if the true toxicity rate is 40% or more then the probability of observing more than 3 toxicities is 62%.

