11.6 Accrual Rate

Accrual is anticipated to be 1-2 patients per month. However, since accrual will stop after the first 6 patients are enrolled, the total time for the study is anticipated 12-15 months.

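### The interim toxicity look is triggered by enrolment of six patients with no stated follow-up, while its 76.7% stopping probability assumes six complete outcomes

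*Combined protocol and SAP*

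**What the plan says.** **Trigger.** Section 11.3.2 states "The design allows for an interim analysis to occur after the first 6 patients are enrolled", and 11.5 repeats it: "As described above an interim analysis will occur after 6 patients are enrolled". The synopsis and 5.1.2 describe six patients as treated at the outset, without saying through which infusion.

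**Rule.** Section 11.3.2: "If 1 or less experience a grade 3-4 toxicity then 4 more will be enrolled". Section 5.1.3: "Enrollment will be suspended if >1/6 or >3/12 patients manifest DLT". Section 5.1.2 acts if more than 1 of 6 "experience greater than grade 3 or 4 toxicity, further enrollment of study subjects and further administration of the study agent will stop" pending a risk assessment.

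**Stated performance.** Section 11.3.2: "if the true toxicity rate is 40% (or higher) then the trial will stop with 76.7% probability", with 11% at a 10% rate. Section 11.4.1 restates the pair (at most 11.4%, more than 76.7%) as the likelihood of stopping early.

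**Pause.** Section 11.6 gives a total of 12-15 months "since accrual will stop after the first 6 patients are enrolled". It states no length for the pause and no condition for restarting.

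**Windows.** Section 8.2.3 uses 30 days from infusion for organ toxicity, 8.2.4 uses 8 weeks for treatment-related death, and 8.2.1 and 8.2.2 give none. None is linked to the interim count.

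**Toxicity horizon.** Section 11.1.1 sets one year, and the synopsis follows toxicity to progression or one year. Section 8.1 and calendar footnote P record adverse events up to 2 months after dosing. The Section 6.0 calendar marks no adverse-event entry at Day 71 or at the visits from Week 18 on, only at off-study/early termination.

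**The concern.** The interim look is the trial's safety gate, and enrolment is not an outcome. Each patient has three infusions (calendar Days 1, 29 and 57). A patient who has only just been enrolled or first treated has contributed little of the period in which toxicity can appear. What is seen least at an early look is toxicity after infusions 2 and 3, and repeat dosing is what this trial adds to the single-infusion study described in 1.4 and 1.5.

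Two teams following the text could take the count on different days and reach different decisions. The 76.7% would describe only one of those choices.

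Two related defects affect the same primary outcome. The event counted changes from section to section, so the probabilities may belong to a rule that is not the one applied. The horizon over which toxicity is to be reported is also longer than the scheduled recording.

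**Working it through.** **1. Reproduce the plan's figures.** Stopping at stage 1 means at least 2 of 6 with toxicity: P(X>=2) = 1 - (1-p)^6 - 6p(1-p)^5.
- p = 0.40: 1 - 0.0467 - 0.1866 = 0.7667 (stated 76.7%).
- p = 0.10: 1 - 0.5314 - 0.3543 = 0.1143 (stated 11% and 11.4%).

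Both reproduce. The formula gives every one of the six the full probability p, that is, a complete outcome.

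**2. When outcomes would be complete.** With no delays, 30 days after infusion 3 is Day 57 + 30 = Day 87, and 8 weeks after it is Day 57 + 56 = Day 113.

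**3. Illustration of an earlier count.** Suppose the count is taken when patient 6 is at Day 31, 30 days past infusion 1. Assume even accrual (gap of 30.4 days at 1/month, 15.2 at 2/month, from 11.6), no infusion delays and a true rate of 40%. Patient i has then been followed for gap x (6-i) + 31 days. Each contributes 0.40 x F(days), where F is the assumed fraction of toxicity that has already appeared. P(at least 2 seen) is the Poisson-binomial tail. The documents give no onset pattern, so four are shown:

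| Assumed onset | 1/month | 2/month |
|---|---|---|
| All within 30 days of infusion 1 | 76.7% | 76.7% |
| Equal thirds on Days 1, 29, 57 | 73.2% | 69.4% |
| Uniform, Day 1 to 87 | 66.2% | 57.9% |
| Uniform, Day 1 to 113 | 60.4% | 45.2% |

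With patient 6 at Day 113, every row returns 76.7%. At a 10% rate no entry exceeds 11.4%, so that ceiling is not breached. These are chances of having seen two events by the look, not of ever stopping.

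**4. Does 12-15 months define the hold?** Time from the first enrolment to the last patient's Day 87:
- 6 + 4 patients, no hold: (9 x gap + 87)/30.4 = 7.4 months (2/month) to 11.9 months (1/month).
- 6 + 4 patients, 87-day hold: (8 x gap + 174)/30.4 = 9.7 to 13.7.
- 12 patients, no hold: (11 x gap + 87)/30.4 = 8.4 to 13.9.
- 12 patients, 87-day hold: (10 x gap + 174)/30.4 = 10.7 to 15.7.

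With four more patients, 12-15 months cannot be reached without a hold. With twelve in total it can. The figure points to a hold but fixes no length.

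**5. Counted event, side by side.** Synopsis and 5.1.3: DLT. Section 5.1.2: toxicity worse than grade 3 or 4. Sections 11.3.2 and 11.4.1, where the probabilities sit: grade 3-4 toxicity, with no window and with grade 5 outside the wording.

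**6. Horizon.** Two months after the Day 57 infusion is about Day 118 (57 + 2 x 30.4), against one year in 11.1.1.

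**The case against.** The best defence has three parts.

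*The pause implies follow-up.* Section 11.6 stops accrual, the look comes after six are enrolled rather than on that day, and the rule counts patients who experience toxicity. This has force. A reader might infer that the count falls on the day patient 6 enrols, untreated, which would cap the chance of stopping at 66.3% (five patients, at least 2 events, 40% rate). The documents do not support that, because the synopsis and 5.1.2 speak of six patients treated. Nor do they support modelling a trial that enrols straight through, since 11.6 rules it out, or six further patients as settled: the synopsis, 5.1.3 and 11.3.2 say four, although totals of 12 also appear. What remains is that the length and end of the pause are unstated.

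*The rule can act later.* Sections 5.1.2 and 5.1.3 carry no look date, so a late second event among the first six could still halt enrolment. On that reading the six eventually trigger the rule with probability 76.7%. A reader might infer that an early look lets a toxic product through undetected; that is not supported. The cost is delay.

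*The one-year rate is not impossible.* Section 8.1 defines adverse events as occurring at any time during the study and records them on an ongoing basis, and the calendar marks them at off-study/early termination. Some late events would therefore be captured. To say that no one-year information could exist goes too far. The scheduled recording does not support a full one-year rate.

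**Conclusion.** The point holds as a gap in specification, not as an arithmetical error. The 76.7% and 11.4% are right for six complete outcomes, and the plan does not secure those outcomes before the count. In the Day 31 illustration the chance of having seen two events at a 40% rate lies between 45% and 77%. One onset pattern shows no loss at all, so the range rests on assumed onset, even accrual and no delays.

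The consequence is a possibly delayed stop. If accrual reopened at that Day 31 look, with the next patient one gap later, patient 6 would still be 56 days from Day 87 and 82 days from Day 113. In that time 1 (56/30.4) to 3 (56/15.2) of the four additional patients could enrol before Day 87, and 2 (82/30.4) to all 4 (82/15.2, capped) before Day 113.

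The differing counted events and the mismatch between the one-year outcome and two-month recording are conflicts on the face of the text and need no assumption. The changes should be made. They are cheap, and they concern the primary outcome.

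**What to change.** 1. In 11.3.2, 11.5 and 11.6, state that the at-most-1-of-6 count is applied, and accrual reopens, only when each of the first six has completed one stated toxicity observation period or has had a qualifying event. The protocol team chooses the period and reconciles it with the differing windows in 8.2.
2. Say how a first-six patient removed early (for example under 5.6.4) is counted.
3. Reconcile the counted event across the synopsis, 5.1.2, 5.1.3, 11.3.2 and 11.4.1, so that the stated probabilities attach to the rule in use.
4. Reconcile the one-year horizon (11.1.1, synopsis) with the recording period (8.1, footnote P) and the calendar.

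**Cost.** Wording, plus a defined hold after patient 6 enrols. If the period ran to the end of the 8.2.3 or 8.2.4 window after infusion 3, the hold would be 87/30.4 = 2.9 or 113/30.4 = 3.7 months. If infusions 2 and 3 were each delayed by the 3 weeks that 5.1.1 allows (42 days in all), it would be 129/30.4 = 4.2 or 155/30.4 = 5.1 months. Section 11.6 already foresees a stop, but its 12-15 month total should be rechecked against the period chosen.
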